5.1.2.1 Other imputations

Incomplete date of initial diagnosis of cancer and date of most recent recurrence

Missing day is defaulted to the 15th of the month and missing month and day is defaulted to 01-Jan.

Incomplete assessment dates for tumor assessment

All investigation dates (e.g. MRI scan, CT scan) must be completed with day, month and year. If one or more assessment dates are incomplete but other investigation dates are available, this/these incomplete date(s) are not considered for calculation of the assessment date and assessment date is calculated as the latest of all investigation dates (e.g. MRI scan, CT scan) if the overall response at that assessment is CR/PR/SD/UNK. Otherwise – if overall response is progression – the assessment date is calculated as the earliest date of all investigation dates at that evaluation number. If all measurement dates have no day recorded, the 1st of the month is used. If the month is not completed, for any of the investigations, the respective assessment will be considered to be at the date which is exactly between previous and following assessment. If a previous and following assessment is not available, this assessment will not be used for any calculation.

Applying the cut-off to tumor assessment

For tumor related assessments, if an evaluation has some assessments done prior to cut-off date and others after the cut-off date, then the evaluation is considered post-cut-off date and will be excluded from analysis.

5.2 AEs coding/grading

Adverse events are coded using the Medical dictionary for regulatory activities (MedDRA) terminology.

AEs will be assessed according to the Common Terminology Criteria for Adverse Events (CTCAE) version 4.03.

The CTCAE represents a comprehensive grading system for reporting the acute and late effects of cancer treatments. CTCAE grading is by definition a 5-point scale generally corresponding to mild, moderate, severe, life threatening, and death. This grading system inherently places a value on the importance of an event, although there is not necessarily proportionality among grades (a grade 2 is not necessarily twice as bad as a grade 1).

5.3 Laboratory parameters derivations

Grade categorization of lab values will be assigned programmatically as per NCI Common Terminology Criteria for Adverse Events (CTCAE) version 4.03. The calculation of CTCAE grades will be based on the observed laboratory values only, clinical assessments will not be taken into account. The criteria to assign CTCAE grades are given in Novartis internal criteria for CTCAE grading of laboratory parameters. The latest available version of the document based on the underlying CTCAE version 4.03 at the time of analysis will be used. For laboratory

tests where grades are not defined by CTCAE v4.03, results will be graded by the low/normal/high (or other project-specific ranges, if more suitable) classifications based on laboratory normal ranges.

A severity grade of 0 will be assigned for all non-missing lab values not graded as 1 or higher. Grade 5 will not be used. For laboratory tests that are graded for both low and high values, summaries will be done separately and labelled by direction, e.g., sodium will be summarized as hyponatremia and hypernatremia.

Imputation Rules

CTC grading for blood differentials is based on absolute values. However, this data may not be reported as absolute counts but rather as percentage of WBC.

If laboratory values are provided as '<X' (i.e. below limit of detection) or '>X', prior to conversion of laboratory values to SI unit, these numeric values are set to X.

The following rules will be applied to derive the WBC differential counts when only percentages are available for a xxx differential

$$\text{xxx count} = (\text{WBC count}) * (\text{xxx \%value} / 100)$$

Further derivation of laboratory parameters might be required for CTCAE grading. For instance, corrected calcium can be derived using the reported total calcium value and albumin at the same assessment using the following formula:

$$\text{Corrected Calcium (mg/dL)} = \text{Calcium (mg/dL)} - 0.8 [\text{Albumin (g/dL)} - 4]$$

In order to apply the above formula, albumin values in g/L will be converted to g/dL by multiplying by 0.1, calcium values in mmol/L will be converted to mg/dL by dividing by 0.2495. For calculation of laboratory CTC grades 0 and 1, the normal range for derived corrected calcium is set to the same limits (in mg/dL) as for calcium.

CTC grades for the derived absolute WBC differential counts (neutrophils, lymphocytes) and corrected calcium will be assigned as described above for grading

Table 5-3 CTC grades for laboratory values in Novartis Oncology (based on CTCAE v4.03 – June 2010)

					CTC Grades ⁽¹⁾				
Lab test (toxicity)	SI unit	Lab test (NCDS)	Normal ranges (Merck manual, July 2015) and conversion factors	0	1	2	3	4	
Hematology									
WBC ↓	10 ⁹ /L	WBC	3.9 – 10.7 x 10⁹/L	≥ LLN	< LLN - 3.0 x 10 ⁹ /L	< 3.0 – 2.0 x 10 ⁹ /L	< 2.0 – 1.0 x 10 ⁹ /L	< 1.0 x 10 ⁹ /L	
WBC (Leukocytosis) ⁽²⁾	10 ⁹ /L	WBC			-	-	> 100 x 10 ⁹ /L	-	
Hemoglobin (Anemia) ⁽²⁾	g/L	HGB	120 - 160 g/L or 7.4 - 9.9 mmol/L (F) 140 - 170 g/L or 8.7 – 10.6 mmol/L (M)	≥ LLN	< LLN - 100 g/L < LLN - 6.2 mmol/L	< 100 - 80 g/L < 6.2 - 4.9 mmol/L	< 80 g/L < 4.9 mmol/L	-	
Hemoglobin ↑	g/L	HGB	(16.113 x mmol/L = g/L)		Increase >0-20 g/L above ULN	Increase >20-40 g/L above ULN	Increase >40 g/L above ULN	-	
Platelets ↓	10 ⁹ /L	PLAT	150 - 350 x 10⁹/L	≥ LLN	< LLN - 75.0 x 10 ⁹ /L	< 75.0 - 50.0 x 10 ⁹ /L	< 50.0 - 25.0 x 10 ⁹ /L	< 25.0 x 10 ⁹ /L	
Neutrophils ⁽³⁾ ↓	10 ⁹ /L	NEUT		≥ 2x10 ⁹ /L	< 2.0 - 1.5 x 10 ⁹ /L	< 1.5 - 1.0 x 10 ⁹ /L	< 1.0 - 0.5 x 10 ⁹ /L	< 0.5 x 10 ⁹ /L	

Lymphocytes (³)↓	10 ⁹ /L	LYM		≥1.5 x10 ⁹ /L	< 1.5 - 0.8 x 10 ⁹ /L	< 0.8 - 0.5 x 10 ⁹ /L	< 0.5 - 0.2 x 10 ⁹ /L	< 0.2 x 10 ⁹ /L
Lymphocytes ↑	10 ⁹ /L	LYM			-	> 4 - 20 x 10 ⁹ /L	> 20 x 10 ⁹ /L	-
Biochemistry								
AST ↑	U/L	AST	0 - 35 U/L or 0 – 0.58 ukat/L (60 x ukat/L = U/L)	≤ ULN	> ULN – 3.0 x ULN	> 3.0 - 5.0 x ULN	> 5.0 - 20.0 x ULN	> 20.0 x ULN
ALT ↑	U/L	ALT	0 - 35 U/L or 0 – 0.58 ukat/L (60 x ukat/L = U/L)	≤ ULN	> ULN – 3.0 x ULN	> 3.0 - 5.0 x ULN	> 5.0 - 20.0 x ULN	> 20.0 x ULN
Total bilirubin ↑	umol/ L	BILI	5.1 – 20.5 umol/L or 0.3 – 1.2 mg/dL (17.1 x mg/dL = umol/L)	≤ ULN	> ULN - 1.5 x ULN	> 1.5 - 3.0 x ULN	> 3.0 - 10.0 x ULN	> 10.0 x ULN
Alk. Phosphatase ↑	U/L	ALP	36 - 92 U/L or 0.5 - 1.5 ukat/L (60 x ukat/L = U/L)	≤ ULN	> ULN - 2.5 x ULN	> 2.5 - 5.0 x ULN	> 5.0 - 20.0 x ULN	> 20.0 x ULN
Creatinine (⁴)↑	umol/ L	CREA T	61.9 - 115 umol/L or 0.7 – 1.3 mg/dL (88.4 x mg/dL = umol/L)	≤ ULN	> ULN - 1.5 x ULN	> 1.5 - 3.0 x ULN	> 3.0 - 6.0 x ULN	> 6.0 x ULN
Creatinine kinase (⁴)↑	U/L	CK	30 - 170 U/L or 0.5 – 2.83 ukat/L (60 x ukat/L = U/L)	≤ ULN	> ULN - 2.5 x ULN	> 2.5 - 5.0 x ULN	> 5.0 - 10.0 x ULN	> 10.0 x ULN
Albumin (²) (Hypoalbumine mia)	g/L	ALB	35 - 55 g/L or 3.5 to 5.5 g/dL	≥ LLN	< LLN - 30 g/L	< 30 - 20 g/L	< 20 g/L	-

Total Cholesterol ↑	mmol/L	CHOL	3.88 – 5.15 mmol/L or 150 - 199 mg/dL (38.67 x mg/dL = mmol/L)	≤ ULN	> ULN - 7.75 mmol/L > ULN - 300 mg/dL	> 7.75 -10.34 mmol/L > 300 – 400 mg/dL	>10.34-12.92 mmol/L > 400 – 500 mg/dL	>12.92 mmol/L > 500 mg/dL
Lipase ↑	U/L	LIPASE	<95 U/L or <1.58 ukat/L (60 x ukat/L = U/L)	≤ ULN	> ULN - 1.5 x ULN	> 1.5 - 2.0 x ULN	> 2.0 - 5.0 x ULN	> 5.0 x ULN
Amylase ↑	U/L	AMYLASE	0 - 130 U/L or 0 – 2.17 ukat/L (60 x ukat/L = U/L)	≤ ULN	> ULN - 1.5 x ULN	> 1.5 - 2.0 x ULN	> 2.0 - 5.0 x ULN	> 5.0 x ULN
Uric acid ⁽²⁾ (Hyperuricemia)	umol/L	URATE	150 - 470 umol/L or 2.5 – 8 mg/dL (59.48 x mg/dL = umol/L)	≤ ULN	> ULN – 10 mg/dL > ULN – 595 umol/L	-	-	> 10 mg/dL > 595 umol/L

ULN = Upper Limit of Normal range; LLN = Lower Limit of Normal range

CTC Grades ⁽¹⁾								
Lab test (toxicity)	SI unit	Lab test (NCDS)	Normal ranges (Merck manual, July 2015) and conversion factors	0	1	2	3	4
Phosphorus ⁽²⁾ (Hypophosphatemia)	mmol/L	PHOS	0.97 – 1.45 mmol/L or 3.0 - 4.5 mg/dL (0.32 x mg/dL = mmol/L)	≥ LLN	< LLN - 2.5 mg/dL < LLN - 0.8 mmol/L	< 2.5 - 2.0 mg/dL < 0.8 - 0.6 mmol/L	< 2.0 - 1.0 mg/dL < 0.6 - 0.3 mmol/L	< 1.0 mg/dL < 0.3 mmol/L

Calcium (corrected) ⁽²⁾ (Hypercalcemia)	mmol/L	CACA LC	2.2 - 2.6 mmol/L or 9 - 10.5 mg/dL (0.2495 x mg/dL = mmol/L)	≤ ULN	> ULN - 11.5 mg/dL > ULN - 2.9 mmol/L	> 11.5 - 12.5 mg/dL > 2.9 - 3.1 mmol/L	> 12.5 - 13.5 mg/dL > 3.1 - 3.4 mmol/L	> 13.5 mg/dL > 3.4 mmol/L
Calcium (corrected) ⁽²⁾ (Hypocalcemia)	mmol/L	CACA LC		≥ LLN	< LLN - 8.0 mg/dL < LLN - 2.0 mmol/L	< 8.0 - 7.0 mg/dL < 2.0 - 1.75 mmol/L	< 7.0 - 6.0 mg/dL < 1.75 - 1.5 mmol/L	< 6.0 mg/dL < 1.5 mmol/L
Magnesium ⁽²⁾ (Hypermagnesemia)	mmol/L	MG	0.62 – 0.99 mmol/L or 1.5 – 2.4 mg/dL (0.4114 x mg/dL = mmol/L)	≤ ULN	> ULN - 3.0 mg/dL > ULN - 1.23 mmol/L	-	> 3.0 – 8.0 mg/dL > 1.23 – 3.3 mmol/L	> 8.0 mg/dL > 3.3 mmol/L
Magnesium ⁽²⁾ (Hypomagnesemia)	mmol/L	MG		≥ LLN	< LLN - 1.2 mg/dL < LLN - 0.5 mmol/L	< 1.2 - 0.9 mg/dL < 0.5 - 0.4 mmol/L	< 0.9 - 0.7 mg/dL < 0.4 - 0.3 mmol/L	< 0.7 mg/dL < 0.3 mmol/L
Glucose (non-fasting) ⁽²⁾ (Hyperglycemia)	mmol/L	GLUC SN	<7.8 mmol/L or <140 mg/dL (0.05551 x mg/dL = mmol/L)	≤ ULN	-	> ULN - 250 mg/dL > ULN - 13.9 mmol/L	> 250 - 500 mg/dL > 13.9 - 27.8 mmol/L	> 500 mg/dL > 27.8 mmol/L
Glucose (fasting) ⁽²⁾ (Hyperglycemia)	mmol/L	GLUC SF	3.9 – 5.8 mmol/L or 70 - 105 mg/dL (0.05551 x mg/dL = mmol/L)	≤ ULN	> ULN - 160 mg/dL > ULN - 8.9 mmol/L	> 160 - 250 mg/dL > 8.9 - 13.9 mmol/L	> 250 - 500 mg/dL > 13.9 - 27.8 mmol/L	> 500 mg/dL > 27.8 mmol/L

Glucose ⁽²⁾ (Hypoglycemia)	mmol/ L	GLUC SN/GL UCSF		≥ LLN	< LLN - 55 mg/dL < LLN - 3.0 mmol/L	< 55 - 40 mg/dL < 3.0 - 2.2 mmol/L	< 40 - 30 mg/dL < 2.2 - 1.7 mmol/L	< 30 mg/dL < 1.7 mmol/L
Potassium ⁽²⁾ (Hyperkalemia)	mmol/ L	K	3.5 - 5.0 mmol/L (0.2558 x mg/dL = mEq/L = mmol/L)	≤ ULN	> ULN - 5.5 mmol/L	> 5.5 - 6.0 mmol/L	> 6.0 - 7.0 mmol/L	> 7.0 mmol/L
Potassium ⁽²⁾ (Hypokalemia)	mmol/ L	K		≥ LLN	< LLN - 3.0 mmol/L	-	< 3.0 - 2.5 mmol/L	< 2.5 mmol/L
Sodium ⁽²⁾ (Hypernatremia)	mmol/ L	SODIU M	136 - 145 mmol/L (0.435 x mg/dL = mEq/L = mmol/L)	≤ ULN	> ULN - 150 mmol/L	> 150 - 155 mmol/L	> 155 - 160 mmol/L	> 160 mmol/L
Sodium ⁽²⁾ (Hyponatremia)	mmol/ L	SODIU M		≥ LLN	< LLN - 130 mmol/L	-	< 130 - 120 mmol/L	< 120 mmol/L
Triglyceride ⁽²⁾ ↑	mmol/ L	TRIG	< 2.82 mmol/L or < 250 mg/dL (0.01129 x mg/dL = umol/L)	< 150 < 1.71	≥ 150 - 300 mg/dL ≥ 1.71 - 3.42 mmol/L	> 300 - 500 mg/dL > 3.42 - 5.7 mmol/L	> 500 - 1000 mg/dL > 5.7 - 11.4 mmol/L	> 1000 mg/dL > 11.4 mmol/L
Coagulation								
INR ⁽²⁾ ↑	1	INR	0.8 - 1.2	≤ ULN	> ULN - 1.5 x ULN	> 1.5 - 2.5 x ULN	> 2.5 x ULN	-
Activated partial thromboplastin time ⁽²⁾ ↑	sec	APTT	25 - 35 sec	≤ ULN	> ULN - 1.5 x ULN	> 1.5 - 2.5 x ULN	> 2.5 x ULN	-

Fibrinogen ⁽⁴⁾ ↓	g/L	FIBRI NO	1.5 – 3.5 g/L or 150 – 350 mg/dL (0.01 x mg/dL = g/L)	≥ LLN	< LLN - 0.75 x LLN	< 0.75 - 0.5 x LLN	< 0.5 - 0.25 x LLN	< 0.25 x LLN

ULN = Upper Limit of Normal range; LLN = Lower Limit of Normal range
 
(1) = LAB CTC grades 1, 2, 3, 4 overrule the study specific (central or local) normal range criteria, e.g. if ULN of Sodium is 151 mmol/L and the value is 151 mmol/L, CTC grade 2 is assigned although the value is ≤ ULN.
 
(2) = Life-threatening consequences and/or hospitalization are not considered for determination of LAB CTC grades 3 and 4. Concomitant usage of anticoagulation therapy (for INR and Fibrinogen) is not considered either.
 
(3) = Values and LNRs for blood differentials can be given as %, absolute values should then be calculated using WBC. Generally, ≥ 1.5 x 10⁹/L (lymphocytes) and ≥ 2 x 10⁹/L (neutrophils) are considered as LAB CTC grade 0
 
(4) = For Creatinine and Fibrinogen, the comparison with baseline is not considered for derivation of LAB CTC grades
 
LAB - CTC grades in Novartis Oncology (26Oct15)
								

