2.8.3 Laboratory data

On analyzing laboratory, data from all sources (central and local laboratories) will be combined. The summaries will include all assessments available for the lab parameter collected no later than 150 days after the last study treatment administration date (see Section 2.1.1).

The following summaries will be produced for hematology and biochemistry laboratory data (by laboratory parameter and treatment):

- Worst post-baseline CTC grade (regardless of the baseline status). Each subject will be counted only for the worst grade observed post-baseline.
- Shift tables using CTC grades to compare baseline to the worst on-treatment value
- For laboratory tests where CTC grades are not defined, shift tables using the low/normal/high/(low and high) classification to compare baseline to the worst on-treatment value.
- Trends of lab parameter values over time (baseline and selected on-treatment timepoints) should be displayed via boxplots based on time windows and corresponding tables displaying the statistics used for the box plots by the selected time points.

The following listing will be produced for the laboratory data:

- Listing of all CTC grade 3 or 4 laboratory toxicities

Liver function parameters

Liver function parameters of interest are total bilirubin (TBL), ALT, AST and alkaline phosphatase (ALP). The number (%) of patients with worst post-baseline values as per Novartis Liver Toxicity guidelines will be summarized:

The following summaries will be produced:

- ALT or AST > 3xULN
- ALT or AST > 5xULN
- ALT or AST > 8xULN
- ALT or AST > 10xULN
- ALT or AST > 20xULN
- TBL > 2xULN
- TBL > 3xULN

- ALT or AST > 3xULN & TBL > 2xULN
- ALT or AST > 3xULN & TBL > 2xULN & ALP < 2xULN

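### SAP Table 5-3 prints the total cholesterol unit conversion in the wrong direction; a mg/dL result converted that way and graded in mmol/L would come out as CTC grade 4

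*SAP*

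**What the plan says.** Table 5-3 in SAP section 5.3 sets out the limits for CTC grading of laboratory values. For total cholesterol the SI unit is mmol/L. The normal range is printed in both units, "3.88 – 5.15 mmol/L or 150 - 199 mg/dL", followed by a rule that multiplies mg/dL by 38.67 to reach mmol/L ("150 - 199 mg/dL (38.67 x mg/dL = mmol/L"). The grade limits also appear in both units:

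- Grade 1: "> ULN - 7.75 mmol/L > ULN - 300 mg/dL"
- Grade 2: "> 7.75 -10.34 mmol/L > 300 – 400 mg/dL"
- Grade 3: ">10.34-12.92 mmol/L > 400 – 500 mg/dL"
- Grade 4: ">12.92 mmol/L > 500 mg/dL"

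The triglyceride row gives its conversion as "0.01129 x mg/dL = umol/L", although its SI unit and its grade limits are in mmol/L.

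Section 5.3 has grades assigned by program from the observed values alone and refers to converting results to SI units. It also says that the criteria come from a sponsor internal grading document, to be used in its latest version at the time of analysis. Section 2.8.3 says that "data from all sources (central and local laboratories) will be combined". It plans tables of worst post-baseline grade, baseline-to-worst shift tables, box plots over time, and a listing of grade 3 or 4 values.

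**The concern.** The cholesterol row contradicts itself. Its two-unit ranges imply one direction of conversion and its stated rule gives the other. This is part of a grading specification rather than background text, so a programmer who follows the rule literally produces a wrong safety grade.

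Worst-grade tables count each subject at the highest post-baseline grade, so one misconverted value is enough to place a subject in grade 4 for cholesterol. The same value would enter the shift table and the grade 3/4 listing. Footnote 1 of Table 5-3 lets the CTC grade override the laboratory's normal range, so a normal flag would not prevent the false grade. Total cholesterol and triglycerides are both in the chemistry panel (Protocol section 7.2.6.6, Table 7-4).

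**Working it through.** **Inputs.** All come from the total cholesterol row of SAP Table 5-3: the factor 38.67 and the five mmol/L and mg/dL pairs printed there.

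**Step 1. Apply the factor in both directions.**

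| mg/dL | mmol/L printed | As written: 38.67 x mg/dL | Reversed: mg/dL / 38.67 | Gap, reversed vs printed |
|---|---|---|---|---|
| 150 | 3.88 | 5,800.5 | 3.879 | -0.03% |
| 199 | 5.15 | 7,695.3 | 5.146 | -0.08% |
| 300 | 7.75 | 11,601 | 7.758 | 0.10% |
| 400 | 10.34 | 15,468 | 10.344 | 0.04% |
| 500 | 12.92 | 19,335 | 12.930 | 0.08% |

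Division reproduces all five pairs to within 0.1%. Multiplication reproduces none. The ratio of the two results is 38.67 x 38.67 = 1,495.4.

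**Step 2. Find the grade that follows from the printed rule.** Grade 4 starts above 12.92 mmol/L. Under the printed rule that limit is reached at 12.92 / 38.67 = 0.334 mg/dL, which is below any realistic cholesterol value. With an upper normal limit of 5.15 mmol/L:

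| mg/dL | mmol/L as written | Grade | mmol/L reversed | Grade |
|---|---|---|---|---|
| 150 | 5,800.5 | 4 | 3.88 | 0 |
| 199 | 7,695.3 | 4 | 5.15 | 0 |
| 250 | 9,667.5 | 4 | 6.46 | 1 |
| 350 | 13,534.5 | 4 | 9.05 | 2 |
| 450 | 17,401.5 | 4 | 11.64 | 3 |
| 550 | 21,268.5 | 4 | 14.22 | 4 |

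**Step 3. Check whether this is a convention of the table.** Nine other rows (bilirubin, creatinine, uric acid, phosphorus, calcium, magnesium, glucose, triglyceride, fibrinogen) were multiplied by their printed factors. Each reproduced its own SI figures, with a largest gap of about 2% (calcium: 0.2495 x 9 = 2.245 against 2.2). The text of section 5.3 also converts calcium from mmol/L to mg/dL by dividing by 0.2495, the correct inverse of that row's rule. Direction therefore carries meaning in this table, and cholesterol is the exception among the rows checked.

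**Step 4. Check triglyceride.** 0.01129 x 250 = 2.82, which is the row's own mmol/L limit. The factor is right and only the umol/L label on the result is wrong.

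**The case against.** The strongest reply is that the misprint may never reach a result.

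- Section 5.3 defers to the latest internal grading document, which may carry the correct factor. This stands: neither document shows what the grading program uses. It is not full reassurance, because the footer of Table 5-3 labels it as the sponsor's own laboratory grading table, dated October 2015. The source could share the error.
- Every cholesterol limit is also printed in mg/dL, so a mg/dL result can be graded with no conversion. This stands, although section 5.3 does mention conversion to SI units, which makes the other route plausible.
- Exposure may be limited. Safety laboratory tests other than urinalysis and pregnancy tests are done centrally. Local results are recorded only when they drove a treatment decision or no concomitant central result exists (Protocol section 7.2.6.6). This narrows the local route, but neither document gives the central or local reporting units. Calling the problem mainly local, or the count small, would be a guess.
- A cholesterol value in the thousands would stand out in the planned box plots and the grade 3/4 listing. That is fair, and it makes an undetected error unlikely.

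Two stronger readings are tempting. A reader might infer that grades go out with no human review, because section 5.3 leaves clinical assessment out of the grade calculation. That sentence concerns how a grade is derived; Protocol section 9.4 provides for data review and queries. A reader might also infer that triglyceride grades are wrong. The row's factor, SI unit and limits all agree on mmol/L, so the documents show no misgrading there.

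**Conclusion.** The printed cholesterol rule is wrong, and the row itself proves it without any outside source. The consequence is conditional: a mg/dL result converted by that rule and then graded in mmol/L becomes grade 4 at any realistic value. Results in mmol/L, or graded on the mg/dL limits, are unaffected.

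Confidence is high for the misprint. It does not extend to any actual misgrading, which depends on the internal document, the program and the laboratories' units. It would go too far to say that the trial's cholesterol grades are wrong, or that all mg/dL results will be reported as grade 4. The number of affected records is unknown. The effect is confined to safety laboratory summaries, so this is a minor correction.

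**What to change.** In Table 5-3, print the cholesterol rule as 0.02586 x mg/dL = mmol/L (1 / 38.67 = 0.02586), or equivalently 38.67 x mmol/L = mg/dL. In the triglyceride row, keep 0.01129 and change the result label to mmol/L. Then check the internal grading document and the grading program on both rows.

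For the cholesterol check, use test values inside each grade band, such as 150, 250, 350, 450 and 550 mg/dL, which should give grades 0 to 4. Values exactly at 300, 400 or 500 mg/dL are poor tests: they convert to 7.758, 10.344 and 12.930, just above the rounded mmol/L limits. The cost is two table entries and one program check.

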5.4 Statistical models

5.4.1 Primary analysis

Analysis of binary data

No formal hypothesis testing will be performed. Responses will be summarized in terms of percentage rates with 95% CIs. An exact binomial confidence interval (implemented using SAS procedure FREQ with EXACT statement for one-way tables) will be calculated [Clopper and Pearson 1934].

SAS procedure FREQ will be used to estimate the proportion of responders (binary outcome = 1 or “Yes”), along with the associated 95% ($=100 \times (1 - 0.05)$) two-sided Pearson-Clopper CI.

5.4.2 Key secondary analysis

Analysis of time to events data

Kaplan-Meier estimates

An estimate of the survival function will be constructed using Kaplan-Meier (product-limit) method as implemented in PROC LIFETEST with METHOD=KM option. The PROC LIFETEST statement will use the option CONFTYPE=LOGLOG.

Kaplan-Meier estimates of the survival function with 95% confidence intervals at specific time points will be summarized. The standard error of the Kaplan-Meier estimate will be calculated using Greenwood’s formula [Collett 1994].

Treatment of ties

The STRATA statement in LIFETEST procedure will be used to analyze time to event data with ties.

5.5 Rule of derivation for immune related criteria

Immune related confirmed irPD is derived as followed:

Confirmed progression 1 (type 1, cPD1) is declared if a patient has 2 consecutive tumor assessments at least 4 weeks (28 days) apart both showing disease progression. Assessments with an irUNK response or irPD assessments < 28 days after initial irPD, are discarded.

The first irPD is flagged as cPD1 while all subsequent irPDs are flagged as xPD1.

Sequence of assessments	Instructions
-------------------------	--------------

1 irPD 2 irUNK 3 irPD (Assessment 1 + 30 days)	
 Assessment 3 is ≥ 28 days after Assessment 1 Assessment 3 represents confirmation of irPD at assessment 1 Assessment 1 irPD is flagged cPD1 Assessment 3 irPD is flagged xPD1
1 irSD 2 irPD 3 irPD (Assessment 2 + 20 days) 4 irPD (Assessment 2 + 30 days)	
 Assessment 3 is < 28 days after Assessment 2 Assessment 4 is ≥ 28 days after Assessment 2 Assessment 4 represents confirmation of irPD at assessment 2 Assessment 2 irPD is flagged cPD1 Assessment 3 and 4 irPDs are flagged xPD1

The date of progression is the date of the assessment flagged as cPD1.

Confirmed progression 2 (type 2, cPD2) is declared if a patient discontinues treatment following a single irPD with no subsequent assessments. Assessments with an irUNK response or irPD assessments < 4 weeks (28 days) after initial irPD, are discarded. Discontinuation of treatment is obtained from EOT case report form.

The assessment is flagged as cPD2 and subsequent irPDs (< 28 days after first PD) are flagged as xPD2.

The table below shows two hypothetical data scenarios and programming instructions.

Sequence of assessments	Instructions
1 irSD 2 irPD - EOT	
 Patient withdraws after initial progression (Assessment 2) without confirmation Assessment 2 irPD is flagged as cPD2
1 irPD 2 irPD (Assessment 1 + 20 days) - EOT	
 Assessment 2 irPD is < 28 days after Assessment 1, so does not represent confirmation However, patient has completed treatment Assessment 1 irPD is flagged cPD2 Assessment 2 irPD is flagged xPD2

The date of progression is the date of the assessment flagged as cPD2.

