4.1.1 Study flow

The study is comprised of the following periods:

[figure not shown]
- Screening
- Treatment

- End of Treatment (EOT)
- Safety follow-up: patients will be followed for safety at 30-Days, 60-Days, 90-Days, 120-Days, and 150-Days after the last dose of PDR001 ([Section 7.1.7](#))
- Post-treatment efficacy follow-up:
 - Before the primary analysis cut-off date (10-Aug-2018), patients who discontinue treatment for reasons other than irRECIST PD will have tumor assessments per [Table 7-1](#) until withdrawal of consent, death, lost to follow-up, or eventual irRECIST PD per BIRC even if new antineoplastic treatment (ANP) is started ([Sections 7.1.8](#) and [Section 7.2.1](#))
 - After the primary analysis cut-off date (10-Aug-2018), post-treatment efficacy follow-up will be discontinued. Therefore, any patients, who are in post-treatment efficacy follow-up at the time of the primary analysis cut-off date, will enter the survival follow-up after completion of the safety follow-up. If clinically indicated, patients may continue to undergo tumor response assessments during the safety follow-up according to local or institutional standard of care; however these tumor response assessments will no longer be reported in the eCRF.
- Survival follow-up: patients will be followed for survival every 3 months after the completion of safety or efficacy follow-up, whichever is last

For a diagram of the study flow, see Figure 4-2. Patients will undergo safety and efficacy assessments during screening, treatment, and follow-up as outlined in [Table 7-1](#) visit evaluation schedule.

This study will use third-party vendors for central imaging, central laboratory, ePRO (e.g., electronic tablet devices to collect patient-reported outcomes (PRO) data), and eligibility checklist plus drug supply management via Interactive Response Technology (IRT). After the primary analysis cut-off date (10-Aug-2018) ePRO and central tumor response assessments will no longer be performed and/or collected.

Figure 4-2 Study flow

*After the the primary analysis cut-off date (10-Aug-2018), post-treatment efficacy follow-up will no longer be performed.

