7.1.8 Follow-up for efficacy evaluations

Patients who discontinue treatment for reasons other than irRECIST PD will have tumor assessments per [Table 7-1](#) until withdrawal of consent, death, lost to follow-up or eventual irRECIST PD per BIRC even if new post treatment ANP is started.

[figure not shown]
After the primary analysis cut-off date (10-Aug-2018), post-treatment efficacy follow-up will be discontinued. Therefore, for patients who discontinue study treatment for any reasons after the primary analysis cut-off date, post treatment efficacy follow-up will not be performed and these patients will enter the safety follow-up. If clinically indicated, patients may continue to undergo tumor response assessments during the safety follow-up according to local or institutional standard of care; however, these tumor response assessments will no longer be reported in the eCRF.

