Immune related duration of overall response (irDOR): For patients with a confirmed irCR or irPR based on BIRC review of tumor assessment data. The start date is the date of first documented confirmed response and the end date and censoring is defined the same as that for time to progression.

Date of confirmed response is derived as followed: Response (irPR or irCR) should be confirmed by a second assessment no less than 4 weeks after the first assessment showing response. Date of response is then the date of the first of these two assessments. For confirmation of irCR the two assessments must be consecutive (intervening assessments of irUNK are permissible). For confirmation of irPR the two assessments do not need to be consecutive, but must not be separated by a pseudo-progression event.

Immune related time to overall response (irTTR) is the time between date of start of treatment until first documented response (confirmed irCR or irPR).

Immune related disease control rate (irDCR) is the proportion of patients with a best overall response of irCR or irPR or irSD. Patients with BOR of irNCRNPD will also be included in DCR if patients with non-measurable disease at baseline are in analysis set.

Immune related progression-free survival (irPFS) is the time from date of start of treatment to the date of event defined as the first documented assessment of irPD that was then confirmed or death due to any cause. Unconfirmed irPD without further adequate tumor assessments will be considered as a confirmed irPD. If a patient has not had an event, progression-free survival is censored at the date of last adequate tumor assessment. An adequate tumor assessment is a tumor assessment with overall response other than irUNK.

Immune related confirmed irPD is derived as described in section 5.5.

Overall survival rate at 1 year and 2 years

OS is defined as the time from date of start of treatment to date of death due to any cause. If a patient is not known to have died, then OS will be censored at the latest date the patient was known to be alive (on or before the cut-off date).

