Progression or death at or before next scheduled Assessment	Date of progression (or death)	Progressed
Progression or death after exactly one missing assessment	Date of progression (or death)	Progressed

Situation	Date	Outcome
Progression or death after two or more missing assessments	Date of last adequate assessment prior to missed assessment	Censored
No progression (or death)	Date of last adequate assessment	Censored
Treatment discontinuation due to 'Disease progression' without documented progression, i.e. clinical progression based on investigator claim	Date of last adequate assessment	Censored
New anticancer therapy given prior to protocol defined progression	Ignore the new anticancer therapy and follow situations above	As per above situations
Death before first PD assessment	Date of death	Progressed

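### SAP 5.5 lets a scan taken after new antineoplastic therapy decide whether an observed irPD counts, so irPFS and irDoR could be lengthened, by an amount the documents do not determine

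*SAP*

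**What the plan says.** **What counts as an event.** SAP 2.7.1 dates irPFS at "the first documented assessment of irPD that was then confirmed or death due to any cause", and adds: "Unconfirmed irPD without further adequate tumor assessments will be considered as a confirmed irPD". irDoR takes its end date and censoring from time to progression, which Protocol Appendix 2, section 6.1.2, also builds on confirmed irPD.

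**How confirmation is derived.** In SAP 5.5, type 1 (cPD1) is "declared if a patient has 2 consecutive tumor assessments at least 4 weeks (28 days) apart both showing disease progression", dated at the first of the two. For type 2: "Confirmed progression 2 (type 2, cPD2) is declared if a patient discontinues treatment following a single irPD with no subsequent assessments". The only scans set aside are these: "Assessments with an irUNK response or irPD assessments < 4 weeks (28 days) after initial irPD, are discarded". A third label, uPD, is reserved for patients still on treatment.

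**Scanning after treatment.** Before the primary analysis cut-off (10-Aug-2018), patients who stop for something other than irRECIST progression are scanned until withdrawal of consent, death, loss to follow-up "or eventual irRECIST PD per BIRC even if new antineoplastic treatment (ANP) is started" (Protocol 4.1.1). Protocol 7.1.8 again sets the end at "eventual irRECIST PD per BIRC even if new post treatment ANP is started".

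**New therapy.** The PFS table in SAP 2.7.3 (Table 2-4) says: "Ignore the new anticancer therapy and follow situations above". SAP 2.7.2 handles the irRECIST endpoints like their RECIST counterparts. By contrast, SAP 2.5.1 uses only assessments before further antineoplastic therapy for best overall response.

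**The concern.** Protocol Appendix 2, section 4.2, recommends confirming irPD chiefly in difficult cases or where pseudo-progression or tumour flare is suspected. A scan under a different drug cannot test that, because shrinkage may be the work of the new drug.

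Ignoring new therapy is harmless in this respect for RECIST 1.1 PFS. There the first documented PD is the event and nothing later can undo it. Once confirmation is required, the same rule lets the next drug undo a progression already recorded on PDR001.

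With no control arm, irPFS will naturally be read against RECIST PFS, and the gap between them taken as benefit after apparent progression. Part of that gap could belong to the next line of treatment. The plan can also disagree with itself: the same early irPD can be a patient's best response, because later scans are excluded there, and still not be an irPFS event.

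**Working it through.** The documents give no event count, median or power for irPFS, so there is no stated figure to reproduce. The check is of the rule itself.

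**1. The SAP's own examples.** Coding SAP 5.5 as written reproduces all four:
- irPD, irUNK, irPD (+30 days): cPD1 at scan 1.
- irSD, irPD, irPD (+20 days), irPD (+30 days): cPD1 at scan 2.
- irSD, irPD, end of treatment: cPD2 at scan 2.
- irPD, irPD (+20 days), end of treatment: cPD2 at scan 1.

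None of the four has a non-progression scan after the irPD or a new-therapy date.

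**2. A hypothetical patient on the 8-week schedule.** irSD day 57, irPD day 113, end of treatment day 120, new drug day 130, irSD days 169 and 225, irPD days 281 and 337. Months are days / 30.4375 (SAP 2.1.1).

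| Rule | All scans available | Data cut at day 240 |
|---|---|---|
| SAP 5.5 as written | cPD1, day 281 (9.2 months) | censored, day 225 (7.4 months) |
| Scans after new therapy not used to confirm or refute | cPD2, day 113 (3.7 months) | cPD2, day 113 (3.7 months) |

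The difference is 281 − 113 = 168 days. uPD does not catch this patient, who is off treatment.

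**3. Direction.** If the scan under the new drug is again irPD (at least 28 days on), cPD1 is dated at the first irPD and nothing changes. If it is irSD or better, the event is delayed or removed. No path shortens irPFS.

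**4. What it takes to lose an irPD.** Appendix 2 (sections 3 and 4.1) measures progression against nadir, the smallest earlier tumour burden. With a nadir of 100 mm, the threshold is 120 mm. A tumour at 140 mm that merely holds its size is still irPD. It must fall below 120 mm, a shrinkage of more than 20/140 = 14%. Only an irPD sitting right at the threshold is lost through a trivial change. For irPD based on non-target or new non-measurable lesions, that progression must reverse.

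**5. Size, under stated assumptions only.** Assume exponential time to first irPD with median 5 months, scans every 8 weeks, and the same median on the next drug. A share *f* of patients switches and keeps being scanned, and a share *r* of those has the irPD reversed at the next scan. The next irPD is then at least two scans later.
- True 6-month irPFS: event-free through the day-168 scan, 168/30.4375 = 5.52 months, 0.5^(5.52/5) = 0.465.
- First irPD at scan 1 (day 56, 1.84 months): 1 − 0.5^(1.84/5) = 1 − 0.775 = 0.225.
- First irPD at scan 2 or 3: 0.775 − 0.465 = 0.310.
- Gain if everyone were affected: 0.310 + 0.225 × 0.775 = 0.484.
- Gain in general: *f* × *r* × 0.484.

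| | *f* = 20% | *f* = 30% | *f* = 50% |
|---|---|---|---|
| *r* = 10% | +1.0 points | +1.5 | +2.4 |
| *r* = 50% | +4.8 | +7.3 | +12.1 |

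Neither *f* nor *r* is in the documents. The range shows only that the answer depends almost entirely on their product.

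**The case against.** **The patient may not be scanned again.** The follow-up sentences in Protocol 4.1.1, 7.1.5 and 7.1.8 cover patients who stop for something other than irRECIST progression. Protocol 7.2.4 requires further scans after central PD only if irRECIST progression has not been met. If one BIRC irPD is enough, no later scan is required and cPD2 gives the right date. Against this, Tables 7-1 and 7-2 continue efficacy follow-up until BIRC has confirmed irRECIST progression, and Protocol 6.1.5.1 ties confirmation to two consecutive assessments. The ambiguity is real. It may make the case uncommon but does not exclude it.

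**Reversal is harder than stabilisation.** This stands (step 4). A reader might infer that stable disease on the next drug is enough to erase an irPD. It is not, and a reversal rate of 50% has no support in the documents. A reader might likewise infer that irPFS *is* materially inflated. The documents support only that it could be.

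**Ignoring new therapy is a declared choice.** It is, and Appendix 1 (section 3.2.10) recommends it. But the same section also recommends a sensitivity analysis that censors before new therapy, and the SAP has none. Nor does the SAP discuss what the choice does once confirmation is required.

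**The endpoint is minor.** irPFS is an other secondary endpoint, descriptive, with RECIST 1.1 PFS reported beside it. irDoR will rest on few patients: the additional efficacy analysis in Protocol 1.2.1.2 had 7 + 1 = 8 RECIST responders. This limits the weight of the point.

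**Best response.** A reader might extend the concern to irRECIST best response. SAP 2.5.1, Appendix 1 section 3.1 and Appendix 2 section 4.3 already keep scans after new therapy out of it.

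**Conclusion.** The gap holds. As written, SAP 5.5 and 2.7.1 let a scan under another drug decide whether a progression seen earlier counts, and the resulting error can only lengthen irPFS and irDoR. It needs a patient with a single irPD who stops PDR001, starts new therapy and is read as irSD or better at the next adequate scan before the cut-off. How many such patients there are depends on how the protocol's follow-up passages are reconciled and on reversal rates the documents do not give. Under the assumed inputs above, 6-month irPFS rises by 1 to 12 points from 46.5%; this is an illustration, not an estimate. The primary ORR, the success rule, RECIST 1.1 PFS and irRECIST best response are not touched. It is a cheap improvement to a secondary endpoint, not a threat to the trial's main conclusion.

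**What to change.** In SAP 5.5 and 2.7.1, for irPFS and irDoR, state that an irPD documented before new antineoplastic therapy may be confirmed or refuted only by assessments made before that therapy starts. A single irPD followed by new therapy before the next adequate scan is cPD2, dated at the irPD. An irPD first seen after new therapy began stays under the existing rule.

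At minimum, pre-specify this as a sensitivity analysis, in line with Appendix 1 section 3.2.10, and report how many patients change status or date.

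Separately, the protocol passages on when scanning ends (7.1.8 and 7.2.4 against Tables 7-1 and 7-2 and section 6.1.5.1) must be reconciled, so that it is clear whether one irPD or a confirmed irPD is meant.

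The cost is one sentence and a date comparison in the derivation. The downside is that a true pseudo-progression in a patient switched early will count as an event. Reporting the number affected shows how much that matters.
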